Subjects: Participants will be 50 abstinent smokers, recruited during pregnancy, who provide written informed consent. We will recruit participants at the “Women’s Center” and its affiliated “Maternal Fetal Medicine High Risk” obstetrical clinics at Yale-New Haven Hospital (YNHH).

Inclusion Criteria: 1) Women with a history of smoking 5+ cigarettes per day that have achieved abstinence defined as no smoking or smoking less than 2 cigarettes per week by 32 weeks’ gestation during pregnancy by 32 weeks gestation; 2) aged 18 to 40 years; 3) able to speak and write English; 4) Edinburgh Postnatal Depression Scale (EPDS) score <10.

Exclusion Criteria: 1) Current substance abuse (e.g., alcohol, benzodiazepines, marijuana); 2) current major depressive disorder, minor depression or dysthymia, or history of any of these disorders in the last 6 months; 3) presence of an Axis I psychotic disorder; 4) plans to relocate out of the area 5) imminent incarceration; 6) planned inpatient hospitalization during study period.

Study Procedures

Overview: We propose to randomize 50 abstinent pregnant smokers to receive either the attentional retraining (AR) or control VP task. Participants will be asked to carry around a smartphone as they go about their daily lives for 2 weeks in their last month of pregnancy (Phase 1). The smartphone will sound an alert randomly during the day, at which time participants will be asked to respond to a short set of questions assessing subjective states; this will be followed by a request to complete the AR (or control) procedures. This same procedure will be repeated for 2 weeks immediately after delivery (Phase 2). Women will undergo a follow-

up visit 3 months after the end of Phase 2, and complete an unmodified VP and follow-up assessments. Given the COVID-19 pandemic screening will be done by phone and study visits, with the exception of Visit 1, will be done via Zoom. If/once it is appropriate to resume in person visits, participants will be offered the option of completing study visits in person at the research clinic or via Zoom.

Screening:

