AR Intervention: Women randomized to AR will be scheduled to complete 2 AR tasks per day. On the AR tasks, the dot always replaces the neutral picture (or word). There is a perfect correlation between picture type and dot location. Consistent with prior work each AR task will target both the initial orienting of attention (40 trials x 200 ms picture presentation) and the disengagement of attention (40 trials x 500 ms picture presentation).⁴² Based on pilot data, the mean duration of AR (and control) assessments is expected to be about 5-7 minutes. There will be 2 types of AR interventions, one targeting smoking-related stimuli and one targeting stress. The type of AR (smoking vs. stress) will alternate daily between the 2 AR tasks. For the smoking AR intervention we plan to use 15 picture sets of consisting of 20 culturally appropriate picture pairs (one smoking-related and one neutral) each. One picture set will be administered on each study day (days 0-14 in pregnancy and days 0-14 postpartum). For the stress AR intervention we plan to use 15 culturally appropriate word sets with 20 word pairs each. Word pairs consist of one emotionally neutral rated word (e.g. book) and an emotionally negative rated word (e.g. fear). We base this on the work of See et al., who demonstrated that AR was effective in inducing attentional avoidance of negative/stressful information (words), thus reducing anxiety related to a naturalistic stressor.⁴⁸ Again one word set will be administered on each study day (days 0-14 in pregnancy/postpartum). To facilitate compliance, a “delay” option will allow women to delay their response by 5 minutes, a “suspend” option will prevent the phone from presenting assessments for a specific time period, and a “make-up” option will allow women to complete trainings if they miss an AR or have technical difficulties (e.g. program crashes and prevents random assessment from being presented). The program is operational independent of internet connectivity, as it will run directly on the smartphone. Data will be stored on the phone and wirelessly backed-up on a server.

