Control Condition: The control task is identical to the AR task in number of tasks per day, number of trials per task (80 trials: 40 x 200ms and 40 x 500ms picture presentation) and the types of tasks: one containing smoking-related and neutral pictures (smoking control task), and one with stress-related and neutral words (stress control task). The only difference is that in the control task, the dot is equally likely to replace the smoking picture (or stress-related word) and the neutral picture (or word). There is a zero correlation between picture type and dot location, therefore there is no effect on AB. This type of control condition has been used in previous AR studies⁷⁷ and in our own pilot study, and ensures that: 1) the duration of AR and control training should not differ; 2) AR and control participants receive equal practice on the motoric aspects of the VP tasks; and 3) AR and control participants are exposed to the same smoking and neutral pictures or stress-related and neutral words. Note that, apart from the number of trials, the control task is the same as the standard VP task.

Attentional Bias Assessment: We will assess attentional bias using the standard VP task on the final random assessment of each day. Consistent with the AR task and prior work,⁴² the VP task will have stimulus presentation durations of 200 ms and 500 ms at each assessment. This will allow us to assess both the initial orienting of attention (20 trials x 200 ms) as well as the difficulty disengaging attention (20 trials x 500 ms), for a total of 40 trials.¹⁷ It will include a balance of both smoking and stress cues. Processing of reaction time data and computation of attentional bias will follow existing procedures.^{22,78} Reaction times (RTs) will be computed from trials with correct responses. We will compute attentional bias scores as the difference in RTs on trials where the probe replaced the smoking picture (or stress-related word) vs. trials where the probe replaced the neutral picture (or neutral word). Faster RTs on the former reflects an attentional bias towards the smoking picture/stress-related word, or vigilance. Faster RTs on

the latter reflects an attentional bias away from the smoking picture/stress-related word, or avoidance.

4. Statistical Considerations: Describe the statistical analyses that support the study design.

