Data Analysis: Given the small sample size and the goal of feasibility, we will plot the potential mediator/moderator covariates and relapse over time. These data will be exploratory only but will provide a rough assessment of the process of relapse (Hypothesis #1) in relation to a number of covariates. We will use Generalized Estimating Equations (GEE)⁷⁹ to evaluate the relationship between the “sad” mood measure and risk of relapse to smoking. For Hypothesis 3 and 4, assuming normal distribution of attentional bias toward smoking and stress cues we will utilize a linear mixed model (LMM) to compare change in the intervention group to change in the control group (see Table 2). Mixed models allow for missing observations and within subject clustering. The best fitting correlation structure will be selected based on Schwartz-Bayesian criterion. We will use all available data in an intention-to-treat analysis. Assessment number and assessment number-group interaction will be included in the model as fixed effects. The overall difference in slopes between the two groups will be tested. Presentation duration, a categorical variable with two levels (200 ms vs. 500 ms), will also be included as a fixed effect. If data are not normally distributed, we will attempt transformation to normality. If data are skewed and comply at zero, we will use a generalized linear mixed model and approximate data by a Poisson distribution, a Zero-Inflated Poisson distribution (ZIP) or a negative binomial distribution. If parametric models are not appropriate, we will use a nonparametric approach for repeated measures. Attentional bias outcomes assessed in the lab will also be examined using LMMs. Analysis for cravings and stress will be similar except that presentation duration factor will not be included; for craving, an additional categorical variable, number of assessment within the day, will be included. We realize that there will be limited power for this statistical analysis but we will be able to detect large effects.

Table 2: Data Analysis Variables

Variable Type	Independent	Dependent			
		Attentional Bias to Smoking Cues	Attentional Bias to Stress Cues	Craving	Stress
Variable	AR vs. Control				
Intervention	Modified VP*	(n/a)	(n/a)	(n/a)	(n/a)
Assessment	(n/a)	VP*	VP*	1-7 scale; cue-provoked	PSS
Modality	Smartphone	Smartphone	Smartphone	Smartphone	Smartphone
Frequency	2	1	1	3	1

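### The Hypothesis 3 and 4 models list neither the urn factors nor the Visit 1 values, and leave unclear whether both arms are forced to a common starting level after training may have begun

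*Combined protocol and SAP*

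**What the plan says.** Section V.4, Data Analysis, uses linear mixed models "to compare change in the intervention group to change in the control group". On the fixed effects it states: "Assessment number and assessment number-group interaction will be included in the model as fixed effects". It adds presentation duration for attentional bias and the number of the assessment within the day for craving. The test is stated as "The overall difference in slopes between the two groups will be tested". For the visit-based task it says only: "Attentional bias outcomes assessed in the lab will also be examined using LMMs". No group main effect, urn factor or Visit 1 value is listed, and the point at which assessment number equals zero is not defined. Table 2 names the AR-versus-control comparison as the independent variable.

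Section V.3, Urn Randomization, balances allocation on age (18–30, over 30), cigarettes per day before conception (1–10, 11 or more) and anxiety disorder. Under Enrollment, a baseline visual probe (VP) task is done at Visit 1, before randomisation. Table 1 also places the PSS and QSU-brief at Visit 1.

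On daily timing, attentional bias is measured "using the standard VP task on the final random assessment of each day", and the 4-item PSS is also on the last assessment of the day. Women in the AR arm are "scheduled to complete 2 AR tasks per day", and the control task matches AR in "number of trials per task (80 trials: 40 x 200ms and 40 x 500ms picture presentation"). For the subjective questions, including craving, the Overview says "this will be followed by a request to complete the AR (or control) procedures".

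**The concern.** There are two separate issues.

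The first is precision. Factors used to balance allocation, and baseline measures of the outcome, normally enter the analysis model. Here they are already collected, and the plan itself concedes limited power.

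The second is meaning. With time and time-by-group but no group term, both fitted lines must meet where assessment number is zero. Randomisation justifies a common mean before training starts. It does not justify one at the end of the first training day. If the lines are pinned there, an early separation between the arms that then stays flat is partly turned into a slope, although the plan says it tests slopes.

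**Working it through.** The plan gives no variance, correlation, alpha or effect size, so there is no stated figure to reproduce.

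**Inputs from the documents.** 50 women, so about 25 per arm (Section V.3, Overview). 84 paid assessments (Section X.2) at 3 per day give 84/3 = 28 daily rows. (Days 0–14 in both phases, under AR Intervention, would give 30.)

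**Assumptions.** Rows coded t = 0 to 27; one line across both phases; complete data; known covariance; between-woman variance σb² = 1; day-to-day SD σe = 1 or 3; random slope absent, or with SD 1 over the course (τ² = 1/27²) and independent of the intercept; covariates explain 10% or 25% of between-woman variance.

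**Training before the first daily row.** AR Intervention gives one picture set and one word set per day. The two daily tasks of 80 trials are therefore one per cue type, so about 80 trials aimed at each bias may come first.

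**Formulas.** The mean of t is 13.5 and S = Σ(t − 13.5)² = 28(28² − 1)/12 = 1827. For one woman's fitted intercept and slope:
- M11 = σe²(1/28 + 13.5²/1827) + σb²
- M12 = −σe² × 13.5/1827
- M22 = σe²/1827 + τ²

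Variance of the slope difference:
- with a group main effect: (2/25) M22
- with the listed terms: (2/25)(M22 − M12²/M11)

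Covariates reduce only σb², which appears only in M11. They therefore cannot change the slope variance once a group term is present.

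**Example (σe = 1, no random slope).** M11 = 1.1355, M12 = −0.007389, M22 = 0.0005473, and M22 − M12²/M11 = 0.0004993. Adding the group term widens the SE by √(0.0005473/0.0004993) = 1.047. If covariates explain 10%, M11 becomes 1.0355 and the listed variance falls to 0.991 of its value.

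**Flat gap.** A constant gap δ with no slope difference gives a listed slope of δ(−M12/M11) per day. With δ = 0.3 this is 0.3 × 0.00651 = 0.00195. The SE is √(0.08 × 0.0004993) = 0.00632, so the shift is s = 0.309 SE. Rejection is Φ(−1.96 + s) + Φ(−1.96 − s) = 6.1%.

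| Setting | Listed slope variance, covariates explain 10% / 25% | SE factor for adding group | Shift from flat 0.3 gap (SE) | Rejection |
|---|---|---|---|---|
| σe 1, random intercept | 0.991 / 0.973 | 1.047 | 0.309 | 6.1% |
| σe 3, random intercept | 0.968 / 0.914 | 1.296 | 0.587 | 9.0% |
| σe 1, plus random slope | 0.998 / 0.993 | 1.013 | 0.160 | 5.3% |
| σe 3, plus random slope | 0.978 / 0.941 | 1.210 | 0.484 | 7.7% |

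With a group main effect the shift is zero. The covariate gain for the slope is then also zero on complete data, and at most 1.1% if 40% stop after 14 rows. What covariates do sharpen is the group term at the origin, whose variance is (2/25) M11: (1.1355 − 0.1)/1.1355 = 0.912 at σe = 1, and (2.2192 − 0.1)/2.2192 = 0.955 at σe = 3, for 10% explained.

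**Type I error.** The planned slope test was simulated with the urn factors omitted and no effect: 12,000 runs, 50 women, random intercept, three binary factors at prevalence 0.5, urn settings assumed. It rejects in 4.4–4.9%.

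**Other settings.** With 15 or 30 rows and intraclass correlation 0.1–0.7, a Visit 1 covariate lowers the listed slope SE by 0.6–6.5% and urn factors (10% explained) by 0–1.7%. Both gains are 0% with a group term, which itself multiplies the SE by 1.00–1.41.

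**The case against.** The strongest reply is that little is at stake. The study states a feasibility goal, the test stays valid, and if Table 2 means that group is a main effect, the covariates add nothing to the slope test. That stands, and it limits the point to a free but small improvement plus a clarification.

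A second reply is that an early jump after training is itself a treatment effect, not a false positive. That also stands. The issue is that it would be labelled a slope, so the group term should be reported alongside the interaction.

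A reader might infer that the smartphone models use no pre-randomisation value at all. The documents do not establish this. The origin is undefined, all available data are to be used, and VP tasks run on the study smartphone. If Visit 1 is the row coded zero, the common start is justified by randomisation.

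It is also tempting to make Visit 1 a shared first row, without a group term, in the daily attentional-bias model. On the label problem that does worse: in the order of the table's settings, it flags a 0.3 SD jump in 9.4, 10.0, 6.1 and 8.3% of trials, against 6.1, 9.0, 5.3 and 7.7%. It also presumes that the Visit 1 task matches the daily one. The Appendix describes 160 trials at 500 ms with smoking pictures only. Attentional Bias Assessment describes 40 trials at 200 and 500 ms with smoking and stress cues.

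A reader might count both daily tasks as 160 trials of exposure. Per cue type it is about 80.

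Craving differs, because its questions precede the training request. Table 2 calls it cue-provoked, however, which leaves its timing relative to cues to be confirmed.

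**Conclusion.** The omission of the urn factors and Visit 1 values is clear from the text. It is not a validity problem, and a reading that it biases the test or inflates type I error is not supported. The forgone gain in slope variance is 0.2–8.6% with the listed terms and about 0% with a group main effect.

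The common-start issue is conditional. It arises only if no group term is intended and the first daily row is the origin, and then only for attentional bias and the 4-item PSS. In that case a flat 0.3 SD gap adds about 0.3 to 4 percentage points to the 5% rejection rate of the slope test. All sizes rest on assumed variances, one row per day and a single line over both phases. The point is worth considering. It does not threaten the trial.

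**What to change.** In Section V.4:

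1. Define assessment number: its zero point, and whether it runs on from pregnancy to postpartum.
2. Add the three urn factors, with the cut-points used for allocation, as fixed effects in every Hypothesis 3 and 4 model.
3. In the smartphone models, add the matching Visit 1 value as a baseline covariate: VP bias score for attentional bias, PSS for stress, and QSU-brief for craving (a proxy for the single 1–7 item). In the lab attentional-bias models, enter Visit 1 VP as the first row with one mean shared by both arms. Use VP in either way only where the Visit 1 task has the same cue type and durations as the outcome, after reconciling Attentional Bias Assessment with the Appendix.
4. In the daily attentional-bias and stress models, include a group main effect so that the interaction is a slope difference, and report the group term with it.

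The cost is a few sentences, up to five degrees of freedom per model (three urn factors, one baseline value, one group term) and no new data. The real price is in item 4: the slope SE widens by an assumed 1–30% in the tabulated settings, and by up to 41% with 15 rows and low intraclass correlation. In those two models the covariates then help the group term, not the slope.

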Intervention Phase 1- Pregnancy: Following enrollment and randomization women will be asked to carry a smartphone as they go about their daily lives and complete 2 random assessments per day and an AB assessment every day for 2 weeks. Random assessments are comprised of questions assessing subjective states (see section d) and the AR (or control) procedure (described below). Data from each of the random assessments and AB assessments are transmitted in real-time allowing compliance to be assessed. If a participant responds to less than 2 random assessments on any study day a research assistant will contact the participant to encourage them to maintain compliance. At the end of the two weeks women will complete Visit 2 via Zoom and complete a post-training unmodified VP task and the Visit 2 assessments outlined in Table 1 and described below. If/once it is appropriate to resume in person visits, participants will be given the option of completing this visit in person at the research clinic.

All EMA procedures and VP tasks will be conducted on a smartphone running an application programmed by Terminal C, a Houston-based company.

Intervention Phase 2- Postpartum: Within 4 days of delivery, women will complete another VP task) and the Visit 3 assessments (Table 1). Participants will be asked to repeat the same procedure as in Phase 1, 2 random assessments per day and an AB assessment every day for 2 weeks. Once again at the end of 2 weeks they will schedule a visit via Zoom and complete an unmodified VP task and Visit 4 assessments. If/once it is appropriate to resume in person visits, participants will be given the option of completing this visit in person at the research clinic.

Post-treatment Visit: Follow-up visits, 5 and 6, will be scheduled 3 and 6 months, respectively, after phase 2. Women will complete an unmodified VP task and the assessments listed in Table 1. Again visits will be done via Zoom; if/once it is appropriate to resume in person visits, participants will be offered the option of completing these visits in person at the research clinic.

Assessments: A summary of the timing of assessments is shown in Table 1.

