Hypothesis		Hypothesis 3a	Hypothesis 4a	Hypothesis 3b	Hypothesis 4b

Note: VP = visual probe; *200 + 500 ms presentation; Frequency = number of tasks/assessments per day

SECTION VI: RESEARCH INVOLVING DRUGS, DEVICES, BIOLOGICS & PLACEBOS

Are there any investigational devices used or investigational procedures performed in a YNHH Operating Room? Yes No *If Yes, please be aware of the following requirements:*

1. **Identification of Drug, Device or Biologic:** What is (are) the **name(s)** of the drug(s), device(s) or biologic(s) being used? Identify whether FDA approval has been granted and for what indication(s).

All protocols which utilize a drug, device or biologic **not** approved by, but regulated by, the FDA must provide the following information: **Not applicable to this research project**

SECTION VII: HUMAN SUBJECTS

1. **Recruitment Procedures:** Describe how potential subjects will be identified, contacted and recruited.

We will obtain referrals from providers in the reproductive health clinics at Yale New Haven Hospital and via the YCCI. YCCI has an ever growing “Help us Discover” database of approximately 8,000 valid email addresses of individuals who have volunteered to be contacted about clinical research at Yale. The emails go out periodically to the database and study teams have found that interest and recruitment for their clinical trial has greatly increased after an email campaign.

Referred women will be contacted by phone by a research assistant who will administer a screening survey to determine provisional eligibility after providing verbal screening consent. In the future, when in person screening is appropriate, pregnant women awaiting a routine visit in the reproductive health clinics at Yale New Haven Hospital will be approached by a research assistant and invited to complete a screening survey to determine provisional eligibility after providing screening consent. We will invite and consent provisionally eligible women to partake in the study. After screening, women who are not eligible will still be offered referrals.

- 1.a Indicate recruitment methods below. Attach copies of any recruitment materials that will be used.

 Flyers (in OB/Gyn clinic)	 Internet/Web Postings	 Radio
 Posters	 Mass E-mail Solicitation	 Telephone

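### The slope test for Hypotheses 3a to 4b names no random effects and leaves the dependence structure to BIC; a woman-level random slope should be fixed in advance

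*Combined protocol and SAP*

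**What the plan says.** Section V.4 specifies a linear mixed model for Hypotheses 3 and 4 and lists its fixed effects: "Assessment number and assessment number-group interaction will be included in the model as fixed effects". For attentional bias, "Presentation duration, a categorical variable with two levels (200 ms vs. 500 ms), will also be included as a fixed effect". For craving, the number of the assessment within the day replaces duration. The test is that "The overall difference in slopes between the two groups will be tested", and Table 2 links the outcomes to Hypotheses 3a, 3b, 4a and 4b.

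On dependence, the section says that mixed models can accommodate clustering within subjects, and then: "The best fitting correlation structure will be selected based on Schwartz-Bayesian criterion". It names no random intercept, random slope, candidate list, standard-error method or degrees of freedom. A random slope is neither required nor excluded.

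The design figures come from Section V.3 and Table 2. The plan is to "randomize 50 abstinent pregnant smokers". Each of the two phases has "2 random assessments per day and an AB assessment every day for 2 weeks". Table 2 gives the daily number of records per outcome ("Frequency = number of tasks/assessments per day"): one for bias to each cue type, one for stress and three for craving.

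**The concern.** The tested quantity is a difference between arms in average slope, so the independent units are the 50 women, not their records. If women have different trajectories, that variation belongs in the standard error. A random intercept, or a structure describing only residual correlation, leaves most of it out. Repeated records then count as nearly independent information about the slope, and the shortfall grows with the number of records.

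The plan leaves this to a choice made after the data are seen. Speaking of a correlation structure invites comparing residual structures only. Even with a random slope among the candidates, BIC penalises it and can reject it when slope variance is moderate. One model carries all four hypotheses, so their false-positive rate could be nominal or several times nominal.

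A secondary gap is the numbering of assessments across phases. The AR Intervention text counts days 0 to 14 separately in each phase, while the payment text in Section X.2 counts 84 assessments in total. Neither defines the model's time variable, yet that variable decides what the overall slope measures.

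**Working it through.** **The plan's own figure.** There is no numeric power or alpha statement to reproduce, only that large effects are detectable. With 25 per arm, one slope per woman and an assumed two-sided 5% level, power for a standardised difference of 0.8 is 80.7% (normal) or 79.1% (exact t). The statement therefore fits a test whose unit is the woman.

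**Records per woman.** Stress: 14 days × 2 phases = 28. Bias, per cue type: 28 × 2 durations = 56. Craving: 28 × 3 per day = 84.

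**Assumptions.** 25 per arm, complete data, independent normal residuals with SD 1, continuous numbering across phases. Slope SD means the between-woman SD of true change from first to last assessment, in residual SDs. The documents do not give it, so a range is shown.

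**Closed form, random intercept only.** τ = SD / (last − first assessment number); R = τ² × Sxx; variance ratio = (1 + R) / (1 + R/(n − 1)); error = 2P(Z > 1.96/√ratio). Sxx is 1827 (28 scores), 3654 (56, two per day) and 49385 (84, numbered 1 to 84).

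Example, 28 scores, SD 0.5: τ = 0.5/27; R = 0.627; ratio = 1.627/1.023 = 1.59; error = 2P(Z > 1.554) = 12.0%.

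| Records | SD 0.1 | 0.25 | 0.5 | 1.0 |
|---|---|---|---|---|
| 28 | 5.3% | 6.8% | 12.0% | 27.4% |
| 56 | 5.6% | 8.6% | 18.7% | 40.4% |
| 84 | 5.8% | 10.2% | 23.6% | 47.5% |

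**Simulation of the BIC rule.** REML, 50 women, random-intercept SD equal to residual SD, group effect fitted, 10,000 replicates per cell. Ranges cover z or t on 48 df and a BIC penalty on women or records.

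| Procedure | Records | SD 0.25 | 0.5 | 1.0 |
|---|---|---|---|---|
| BIC among compound symmetry, AR(1), both | 28 | 6.2–6.8% | 10.4–11.5% | 23.0–25.0% |
| | 56 | 8.2–9.0% | 17.8–19.1% | 35.2–36.7% |
| | 84 | 10.1–11.0% | 21.7–23.3% | 41.9–43.4% |
| BIC, random slope added as candidate | 28 | 5.8–6.8% | 6.1–10.1% | 5.2–6.0% |
| | 56 | 6.9–9.0% | 5.5–9.4% | 4.6–5.1% |
| | 84 | 7.1–10.7% | 5.0–6.7% | 5.1–5.6% |

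A random slope fixed in advance gave 3.9–5.4% with t on 48 df (50 women − 2 arms) across SD 0.1 to 1.0, and 4.4–6.0% with z. AR(1) alone was conservative in most cells (0–2.4% with 28 scores), but BIC chose it in under 0.5% of trials. That conservatism needs large differences in level between women: with random-intercept SD 0.3 and 56 scores, AR(1) alone gave 11.5–12.3% at SD 0.5.

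**Serial correlation.** With 30 daily scores, random-intercept SD 0.7, slope SD 0.5 and autocorrelation 0.3, BIC chose random intercept plus AR(1) in about 100% of trials even with a random slope as candidate, and error was 10.1%. A fixed random slope with independent residuals gave 7.1% (z) or 5.9% (48 df). In a further simulation (28 scores, 500 replicates per cell), a fixed random slope with BIC choosing only the residual structure and 48 df gave 3.6–6.4% in every cell, including autocorrelation 0.3.

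**Numbering.** On a 1–28 axis the phase means are 7.5 and 21.5 and the overall mean is 14.5. The between-phase part of Sxx is 28 × 7² = 1372, and 1372/1827 = 75.1%. So about 75% of the overall slope's weight is the Phase 2 minus Phase 1 contrast. If numbering restarts in Phase 2, that share is 0%.

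**The case against.** The strongest reply is that this is missing detail, not a demonstrated error. The plan names a mixed model, mentions clustering and fixes an objective selection rule that does not exclude a random slope. Large inflation needs substantial slope variance and no random slope in the fitted model, and the documents support no value for that variance. This stands as a limit on size: the figures are ranges, not expected error rates. It is strongest for bias. The daily task has 40 trials and "It will include a balance of both smoking and stress cues"; split over 2 durations, 2 cue types and 2 probe positions, that leaves 40/8 = 5 trials per cell. Residual noise is then large and the low end of the range more plausible. The same argument does not cover craving or stress.

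BIC's behaviour also depends on implementation. With 28 scores and SD 0.5 it chose the random slope in 15% of trials under one set-up (slope covariance included, penalty on records). With 30 scores and a penalty of log(50) it did so in 58%, with 5.9% error. A protection that varies this much with unstated details is itself a reason to specify.

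Two points on the remedy stand. Kenward-Roger and robust errors were not simulated; the near-nominal figures are for t on 48 df. The slope variance will also often be estimated as zero: by calculation, in about 48% of trials at SD 0.1 and 27% at SD 0.25 with 28 scores, and 43% and 11% with 56. The SAP should say what happens then. The feasibility aim and the admission of limited power do not answer the point, because a false positive in a pilot still misdirects later work.

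**Conclusion.** The concern holds, with medium confidence, as a cheap improvement. Following the stated rule can understate the standard error of the slope difference for all four hypotheses. With only residual structures competing, error is about 10 to 23% at slope SD 0.5, depending on the number of records. With a random slope as a candidate it reaches about 11% at worst when residuals are independent. If women's slopes hardly differ, there is no material inflation. These sizes rest on the assumed slope SDs, 25 per arm, complete data, normal outcomes and a two-sided 5% level, which the plan does not state. The numbering point is secondary and concerns what is estimated rather than the error rate.

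**What to change.** In Section V.4, for the normal-outcome models of Hypotheses 3a to 4b:

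1. Keep the overall slope difference as the primary test. Fix in advance a woman-level random intercept and a random slope for assessment number. Let BIC choose only the residual structure, from a listed set. Name one inference method, either Kenward-Roger or small-sample-corrected robust standard errors, and the degrees of freedom if the slope variance is estimated as zero (the simulations used 48 throughout).
2. Add a fallback. If the model does not converge, drop the intercept-slope covariance. If it still fails, use the random-intercept model with small-sample-corrected cluster-robust standard errors.
3. If the count or zero-inflated route is taken, include the same random effects. Kenward-Roger and the figures here do not carry over to it.
4. State how assessments are numbered across phases. Report group-by-phase and phase-specific slopes as secondary or sensitivity estimates, not as replacements for the primary test.

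The cost is SAP wording and a few lines of code. If slopes do not vary, a test with 80% power (noncentrality 2.802) falls to 78.4% on 48 df, and intervals widen by 2.011/1.960 = 1.026, about 3%. If slopes do vary, intervals widen to their honest width, by √ratio × 1.026. At SD 0.25 / 0.5 / 1.0 that is 1.10 / 1.29 / 1.84 (28 scores), 1.17 / 1.52 / 2.41 (56) and 1.23 / 1.70 / 2.81 (84).
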